4.3. End of Study Definition

A subject is considered to have completed the study if he/she has completed the last scheduled procedure shown in the Schedule of Activities (SoA) (Section 1.3 and Section 1.4), including the Survival Follow-up of up to 1 year after the last subject is enrolled and dosed.

The end of the study is defined as the date of the last scheduled procedure shown in the SoA (Section 1.3 and Section 1.4) for the last subject in the study.

5. STUDY POPULATION

Prospective approval of protocol deviations to recruitment and enrollment criteria, also known as protocol waivers or exemptions, is not permitted.

5.1. Inclusion Criteria

Subjects may be eligible for inclusion in the study if they meet the following criteria:

1. Must be a male or female subject \geq 18 years of age
2. Must have histologically or cytologically-confirmed R/M HNSCC of the oral cavity, oropharynx, hypopharynx, or larynx that is considered incurable by local therapies.
3. Must be eligible for pembrolizumab monotherapy based on the current prescribing information for pembrolizumab ([Keytruda 2019](#)): (a) for first-line treatment, subjects with metastatic or with unresectable, recurrent HNSCC whose tumors express PD L1 (CPS \geq 1) as determined by an FDA-approved test; (b) subjects with R/M HNSCC with disease progression on or after platinum-containing chemotherapy, regardless of PD-L1 expression.
4. Must have had 0 to 2 prior therapies for R/M HNSCC. Therapy for locally or regionally advanced HNSCC with or without radiation therapy is not counted as a line of therapy unless recurrence and/or metastasis was demonstrated $<$ 6 months from the end of such therapy.
5. Must have at least 1 measurable lesion (which has not been previously irradiated) according to RECIST v 1.1 ([Eisenhauer 2009](#)).
6. For Stage 1 only: Must have at least 1 other lesion that can be biopsied
7. For Stage 1 only: Must be willing to undergo a pretreatment and on-treatment biopsy of the available tumor lesion (described in inclusion criterion #6). Archival tissue (up to 6 months before the first dose of duvelisib) may be considered in place of the required pretreatment biopsy after consultation with the Sponsor, as long as no intervening systemic regimen had been taken during that time frame.
8. Must provide prior data on PD-L1 expression and HPV status, if available
9. Must have adequate organ function defined by the following laboratory parameters:
 - a. Adequate bone marrow reserve as evidenced by:
 - Absolute neutrophil count (ANC) $\geq 1.5 \times 10^9/L$
 - Platelet count $\geq 100 \times 10^9/L$
 - Hemoglobin level $\geq 9.0 \text{ g/dL}$
 - b. Adequate renal function as evidenced by:
 - a serum creatinine level $< 1.5 \text{ mg/dL}$, or
 - estimated creatinine clearance value of $\geq 60 \text{ mL/min}$ (as determined by the Cockcroft-Gault method) for subjects with creatinine levels $> 1.5 \times$ institutional upper limit of normal (ULN)

- c. Adequate hepatic function as evidenced by:
 - Total bilirubin level $\leq 1.5 \times$ ULN (exception: subjects with Gilbert's Syndrome may have a bilirubin level $> 1.5 \times$ ULN)
 - AST/serum glutamic-oxaloacetic transaminase (SGOT) and ALT/serum pyruvic transaminase (SGPT) levels $\leq 2.5 \times$ ULN or $\leq 5 \times$ ULN in subjects with liver metastases
- 10. Must have international ratio (INR) or prothrombin time (PT) and activated partial thromboplastin time (aPTT) $\leq 1.5 \times$ ULN, unless subject is receiving anticoagulant therapy in which case PT or aPTT must be within therapeutic range of intended use of anticoagulants
- 11. Must have an Eastern Cooperative Oncology Group (ECOG) performance status ≤ 1
- 12. For male and female subjects of reproductive potential (i.e., not surgically sterile or female subjects who are not postmenopausal), must be willing to use a highly effective method of contraception (see Section 10.4) for the duration of the study interventions and for at least 4 months after the last dose of study interventions
- 13. Must have a negative serum human chorionic gonadotropin (hCG) pregnancy test result within 7 days before first dose of duvelisib if the subject is a woman of childbearing potential (WCBP) (defined in Section 10.4)
- 14. Must provide signed and dated institutional review board (IRB)/independent ethics committee (IEC)-approved informed consent form (ICF) before any study-specific screening procedures are performed

5.2. Exclusion Criteria

Subjects will be excluded from the study if they meet any of the following criteria:

1. Have disease that is suitable for local therapy administered with curative intent
2. Have been previously treated with 3 or more systemic regimens given for recurrent and/or metastatic disease
3. Have received anticancer treatment, major surgery, or any investigational drug within 30 days or 5 half-lives, whichever is shorter, before the start of study intervention
4. Have received radiation therapy within 14 days prior to the first dose of duvelisib in this study, including, in addition (if necessary), the timeframe for resolution of any actual or anticipated toxicities from such radiation. Palliative radiation therapy is allowed if > 7 days before first dose of duvelisib and any toxicity is \leq Grade 1.
5. Have received prior radiation therapy to $> 25\%$ of bone marrow-bearing areas
6. Have co-existing head-and-neck carcinoma of the nasopharynx, squamous cell carcinoma of unknown primary, salivary gland tumors, or any other non-squamous primary tumors involving the head and neck
7. Have received previous treatment with a PI3K inhibitor
8. Have received previous treatment with a PD-1 or PD-L1 inhibitor

9. Have received organ or allogenic bone marrow or peripheral blood stem cell transplant
10. Have a history or concurrent condition of interstitial lung disease of any severity and/or severely impaired lung function
11. Have a prior history of drug-induced colitis or drug-induced pneumonitis
12. Have active cytomegalovirus (CMV) or Epstein-Barr virus (EBV) infection (subjects with detectable viral load)
13. Have an infection with hepatitis B or hepatitis C:
 - Subjects with a positive hepatitis B surface antigen (HBsAg) or hepatitis C antibody (HCVAb) will be excluded
 - Subjects with a positive hepatitis B core antibody (HBcAb) must have negative hepatitis B virus (HBV) DNA to be eligible and must be periodically monitored for HBV reactivation by institutional guidelines
 - Investigators who strongly believe that a positive HBcAb is false-positive due to passive immunization from previous immunoglobulin infusion therapy should discuss the potential to defer HBV prophylaxis with the Medical Monitor
14. Have a history of or known human immunodeficiency virus (HIV) infection
15. Have a history of tuberculosis treatment within the 2 years prior to first dose of duvelisib
16. Have a history of chronic liver disease or veno-occlusive disease/sinusoidal obstruction syndrome
17. Have known psychiatric or substance abuse disorders that would interfere with cooperation with the requirements of the study
18. Are receiving ongoing treatment with chronic immunosuppressants (e.g., cyclosporine) or systemic steroids > 20 mg of prednisone (or equivalent) per day
19. Have an active infection or are receiving ongoing systemic treatment for a clinically significant bacterial, fungal, or viral infection at Screening

NOTE: Subjects on antimicrobial, antifungal, or antiviral prophylaxis are not specifically excluded if all other inclusion/exclusion criteria are met

20. Have received a live or live attenuated vaccine within 6 weeks of first dose of duvelisib
21. Have received medications or consumed foods that are strong inhibitors or inducers of cytochrome P450 3A (CYP3A) (Section 10.2) within 2 weeks prior to the first dose of duvelisib or concurrent with duvelisib treatment
22. Are unable to receive prophylactic treatment for pneumocystis, herpes simplex virus (HSV), or herpes zoster (VZV) at screening
23. Have had prior surgery (e.g., gastric bypass surgery, gastrectomy) or gastrointestinal dysfunction that may affect drug absorption
24. Have any active gastrointestinal dysfunction interfering with the subject's ability to be administered oral medications
25. Is a female subject who is pregnant or breastfeeding

26. Have a baseline QT interval corrected using the Fridericia correction method (QTcF) > 500 ms (average of triplicate readings). NOTE: This criterion does not apply to subjects with a right or left bundle branch block.
27. Have New York Heart Association Class III or IV congestive heart failure
28. Have a history of another active malignancy that is progressing or requires active treatment. Exceptions include adequately treated non-melanoma skin cancer, curatively treated in-situ cancer of the cervix, or other solid tumors curatively treated with no evidence of disease for > 3 years.
29. Have known active central nervous system metastases and/or carcinomatous meningitis. Subjects with previously treated brain metastases may participate provided they are stable (without evidence of progression by imaging for at least 4 weeks prior to the first dose of duvelisib and any neurologic symptoms have returned to baseline), have no evidence of new or enlarging brain metastases, and are not using steroids for at least 7 days prior to the first dose of duvelisib. The exception does not include carcinomatous meningitis.
30. Have an active autoimmune disease requiring systemic treatment within the last 3 months prior to first dose of study intervention, documented history of clinically severe autoimmune disease, or a syndrome that requires systemic or immunosuppressive agents except vitiligo, Type 1 diabetes mellitus, hypothyroidism stable on hormone-replacement therapy, Sjogren's syndrome, and resolved childhood asthma/atopy. Subjects who require intermittent use of bronchodilators, inhaled steroids, or local steroid injections may participate in this study.
31. Have a history of stroke, unstable angina, myocardial infarction, or ventricular arrhythmia requiring medication or mechanical control within the last 6 months prior to first dose of duvelisib
32. Have an unstable or severe uncontrolled medical condition or any important medical illness or abnormal laboratory finding that would, in the Investigator's judgment, increase the subject's risk to participating in this study

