Physical Examination	X	X	X		X	X	X		See Section 8.2.1. Full examination (including height) at Screening and symptom-directed at subsequent time points. Screening results can be used for C1D1 if assessments are performed within 7 days of first dose.
Vital Signs and Weight	X	X	X	X	X	X	X	X	See Section 8.2.1. Vital signs measured with subject in a semi-supine position after 5 minutes rest. Includes temperature, systolic and diastolic blood pressure, pulse rate, and respiratory rate.
ECOG Performance Status	X	X	X	X	X	X	X	X	See Section 8.3.1. Screening ECOG results can be used for C1D1 if test is performed within 7 days of first dose.

		Duvelisib Lead-in	Duvelisib in Combination with Pembrolizumab ^a				End of Treatment and Follow-up			
Activity ^b	Screening (D-30 to D -1)	Cycle 1 (4 weeks)			Cycle 2 and Cycle 3 (3 weeks)	Cycles ≥ 4 (3 weeks)	EoT ^c	Safety F/U 30 D (+7) postdose) ^d	Survival F/U Every 3 months until End of Study	Notes
		W1	W2	W3	W1	W1				
		D1	D8 ± 5	D15 ± 3	D1 ± 3	D1 ± 3				
ECG (12-lead)	X									See Section 8.2.2. ECG at Screening will be performed in triplicate. QTc measurements will use the Fridericia correction method. Additional on-treatment ECGs should be performed per the Investigator's discretion as clinically indicated.
Concomitant Medications and Procedures		Ongoing								See Section 6.5.1 for required and recommended prophylaxis. Concomitant medications and procedures occurring within 30 days before first dose will be recorded at Screening.
AE/SAE Assessment		Ongoing								See Section 8.4 for AE management. See Section 8.4.3 for reporting requirements.
Coagulation tests	X									PT, aPTT, and INR. See Table 23.
Viral Screening	X									Hepatitis serology: HCVAb, HBsAg, HBcAb. HPV testing (if status not available at Screening). CMV/EBV serology or viral load. HIV test is not required if a prior negative test within 9 months is available. See Table 23.
CMV Reactivation Monitoring (if applicable)			X		X	X				Subjects with a history of CMV infection should be monitored for reactivation by PCR at least monthly. See Section 6.5.1.
C-Reactive Protein	X	Obtain when Grade ≥ 2 diarrhea, any grade colitis, or any grade immune-mediated toxicity (e.g., pneumonitis, colitis, hepatitis, endocrinopathies, nephritis/renal dysfunction, cutaneous adverse reactions, encephalitis) occurs								See Table 23.
T3, FT4, and TSH	X				X	X		X		Every other cycle starting at C2D1.

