6.5.1. Required and Recommended Prophylaxis

Based on the duvelisib clinical experience to date, the following are required or recommended:

- Subjects are required to receive pneumocystis prophylaxis concomitant with duvelisib treatment per institutional guidelines. After completion/discontinuation of duvelisib treatment, continue prophylaxis until the absolute CD4+ T-cell count is greater than 200 cells/ μ L.
- HSV and VZV infections have been observed with duvelisib; therefore, herpes (HSV/VZV) prophylaxis concomitant with treatment is recommended, per Investigator discretion according to institutional guidelines
- Subjects with a history of CMV infection/reactivation or viremia should be monitored for reactivation by polymerase chain reaction (PCR) or antigen test at least monthly. Prophylactic treatment per institutional guidelines is recommended for subjects considered by Investigators to be at high risk for CMV reactivation.
- Antimicrobial prophylaxis and pneumococcal pneumonia vaccine are recommended for subjects with history of or considered at high risk for infections and during periods of severe neutropenia. Choice of antimicrobial agent (antifungal, antibiotic, antiviral) is per Investigator discretion, but the restrictions on the use of CYP3A inducers, inhibitors, and substrates should be considered (see Section [6.5.2](#)).

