6.6.2. Recommended Duvelisib Dose Modifications for the Management of Duvelisib Toxicities

The dose level of duvelisib may be modified to manage duvelisib toxicities ([Table 12](#)) or overlapping toxicities in combination with pembrolizumab ([Table 10](#)).

Non-hematologic and hematologic AEs for duvelisib for non-overlapping toxicities in combination with pembrolizumab should be managed with supportive care, treatment hold, dose reduction, or discontinuation of duvelisib as described in [Table 12](#). Additional information regarding management of duvelisib toxicities can be found in the Summary of Data and Guidance to the Investigator section of the duvelisib IB.

Refer to [Table 11](#) for dose level modifications recommended for duvelisib. Subjects who have a duvelisib dose reduction due to a toxicity will not be eligible for a dose re-escalation.

Any subject who develops an unacceptable toxicity at the 15 mg BID dosage of duvelisib should discontinue the study interventions.

Duvelisib may be held up to 42 days due to toxicity. While duvelisib is being held, the subject may continue to receive pembrolizumab at the discretion of the Investigator. Doses held for > 42 days due to treatment-related toxicity will result in permanent discontinuation of duvelisib.

If duvelisib is discontinued, the subject will also discontinue pembrolizumab and proceed with their End of Treatment (EoT) Visit.

Table 11: Duvelisib Dose Level Modifications for Toxicities

Dose Level	Duvelisib
Starting Dose	25 mg BID PO
-1	15 mg BID PO ^a

Abbreviations: BID: twice daily; PO: oral.

^a Discontinue duvelisib if subject is unable to tolerate duvelisib 15 mg BID.

Table 12: Recommended Duvelisib Dose Modifications for the Management of Duvelisib Toxicities

Toxicity	Adverse Reaction Grade	Dose Modification and Recommended Management
Non-hematologic Adverse Reactions		
Infections	Grade 3 or higher infection	
 Withhold duvelisib until resolved Resume at the same or reduced dose (see Table 11)
	Clinical CMV infection or viremia (positive PCR or antigen test)	
 Withhold duvelisib until resolved Resume at the same or reduced dose (see Table 11) If duvelisib is resumed, monitor subjects for CMV reactivation (by PCR or antigen test) at least monthly
	PJP	
 For suspected PJP, withhold duvelisib until evaluated

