Other Screening Tests	
 Viral screening: serology (hepatitis B surface antigen [HBsAg], hepatitis B core antibody [HBcAb], hepatitis C virus antibody [HVCAb], Epstein-Barr virus [EBV] antibody, human immunodeficiency virus [HIV] antibody); HPV testing (if status not available at Screening), cytomegalovirus (CMV) via serology, or viral load detection via polymerase chain reaction (PCR). Subjects with a negative HBsAg and positive HBcAb require an undetectable/negative hepatitis B DNA test (e.g., PCR test) to be dosed. 
 HIV testing is required for subjects without documentation of a prior negative test result from within the last 9 months. Results will be analyzed locally and will not be captured in the study database. Only subjects with negative results will be eligible to begin study intervention. Coagulation tests: prothrombin time (PT), activated partial thromboplastin time (aPTT), and international normalized ratio (INR) C-reactive protein^b Triiodothyronine (T3), free thyroxine (FT4), and thyroid-stimulating hormone (TSH) Food and Drug Administration (FDA)-approved PD-L1 testing is required for indications specified in the current pembrolizumab prescribing information (Keytruda 2019), unless results are already available. Information on FDA-approved tests is available at: http://www.fda.gov/CompanionDiagnostics.

NOTES:

- Details of liver chemistry stopping criteria and required actions and follow-up assessments after liver stopping or monitoring event are provided in [Table 12](#) for duvelisib and in [Table 13](#) for pembrolizumab. All liver-related SAEs must be reported as described in Section [8.4.3](#).
- A serum pregnancy test must be performed within 7 days of the first dose. At subsequent time points, serum testing is preferred but urine testing is allowed if a blood draw for other assessments is not performed. A positive urine test result must be confirmed by a serum test.

^a See Section [8.2.4](#) for guidance on repeating/recording laboratory tests with values that are considered clinically significant or that require a change in subject management.

^b Also obtain when Grade ≥ 2 diarrhea, any grade colitis, or any grade immune-mediated toxicity (e.g., pneumonitis, colitis, hepatitis, endocrinopathies, nephritis/renal dysfunction, cutaneous adverse reactions, encephalitis) occurs.

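### Exclusion 12 turns on a detectable CMV or EBV viral load, but the required screening tests need not measure viral load, so a subject with undetected viremia can be dosed

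*Combined protocol and SAP*

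**What the plan says.** Exclusion criterion 12, worded the same in the synopsis and in Section 5.2, bars subjects who "Have active cytomegalovirus (CMV) or Epstein-Barr virus (EBV) infection (subjects with detectable viral load"). The bracket makes viral load the defining measurement for both viruses.

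The tests that serve this criterion are set out in three places:

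- Table 1 (Section 1.3, Stage 1) and Table 3 (Section 1.4, Stage 2), Viral Screening row: "CMV/EBV serology or viral load".
- Table 23 (Section 10.3), Other Screening Tests, for CMV: "cytomegalovirus (CMV) via serology, or viral load detection via polymerase chain reaction (PCR").
- The same cell of Table 23, inside the serology bracket, for EBV: "Epstein-Barr virus [EBV] antibody".

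For hepatitis B, that cell goes a step further: "Subjects with a negative HBsAg and positive HBcAb require an undetectable/negative hepatitis B DNA test (e.g., PCR test) to be dosed".

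On treatment, Table 12 (Section 6.6.2) lists "Clinical CMV infection or viremia (positive PCR or antigen test") among the infections for which duvelisib is withheld. Section 6.5.1 adds: "Subjects with a history of CMV infection/reactivation or viremia should be monitored for reactivation".

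**The concern.** An antibody result and a viral load are different measurements. A positive antibody shows that the subject has met the virus; it does not show whether virus is detectable now. A site that takes the serology option has done what the schedule asks, yet holds no value on which exclusion 12 can be decided for a seropositive subject.

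What is at stake is subject safety and the consistency of eligibility decisions. Section 2.4.1 lists infections among the important identified risks of duvelisib, and the sponsor wrote exclusion 12 to keep viremic subjects out. If the required tests do not have to reveal viremia, that protection depends on which option a site picks. A subject with CMV viremia at entry could start duvelisib while already in a state that Table 12 treats as a reason to withhold it. Sites would also apply the criterion unevenly: one measuring viral load would exclude a subject whom another, using antibody alone, would admit.

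**Working it through.** No arithmetic applies, because the documents give no seroprevalence and no rate of viremia. The check sets the criterion beside the required tests and then looks for text that would close the gap.

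**1. Does a required test measure what the criterion is defined on?**

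| Virus | Exclusion 12 | Tables 1 and 3 | Table 23 |
|---|---|---|---|
| CMV | detectable viral load | serology or viral load | serology or PCR |
| EBV | detectable viral load | serology or viral load | antibody |

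In every cell of the two right-hand columns, serology alone completes the requirement. For EBV, Table 23 on its natural reading offers nothing else, so it also disagrees with Tables 1 and 3, which do offer viral load. The PCR phrase that ends the Table 23 sentence could be read to reach back to EBV. It would still be joined by \"or\" in sense, as an alternative, so serology would still suffice.

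**2. Does any other text require a viral load before the first dose?**

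- Exclusion 19 (Section 5.2) bars active infection at Screening but attaches no viral-load test.
- Section 8 requires screening results to be reviewed against all eligibility criteria but names no further test. Sections 5 and 8 do not permit waivers, so the criterion binds every subject.
- Section 10.3 lets the investigator add tests judged necessary. That is permission, not a requirement.
- The CMV reactivation row in Tables 1 and 3 applies only to subjects with a history of CMV and is not marked at Screening. Its first mark is C1D8 in Stage 1, a week after the first duvelisib dose, and C1D1 in Stage 2. There is no EBV counterpart.

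None of these requires the measurement.

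**3. Does the document handle a similar case differently?** Yes. For hepatitis B, a positive core antibody leads to a DNA test that must be negative before dosing (exclusion 13 and Table 23). No such second step is written for CMV or EBV.

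**4. Result.** A subject with undetected CMV or EBV viremia can complete every required screening test by serology and be dosed, although exclusion 12 bars that subject. For CMV, the same state is a withholding condition in Table 12. The infection rows of Table 12 do not name EBV, so that link holds for CMV only.

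**The case against.** The best reply is that a careful site can apply the criterion within the text as it stands. Viral load is a listed option for both viruses in Tables 1 and 3, Section 10.3 allows additional tests, Section 8 obliges the site to confirm every criterion, and waivers are barred. Serology first, with viral load when it is positive, is compatible with all of this. A subject known to be viremic remains excluded.

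That reply stands against one stronger reading, that a site using serology is unable to apply exclusion 12. It is able to, by ordering a PCR. The reply does not remove the mismatch, because nothing makes the site take that step.

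Three further inferences are tempting, and the documents do not support them:

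- *That most of the 30 planned subjects would enter unassessed.* This needs an assumed seroprevalence, and the assumption that every site chooses serology and none adds a PCR. It would also count seropositive subjects, not viremic ones.
- *That undetected viremia would distort the dose-limiting toxicity assessment.* This requires undetected viremia in one of the first 6 subjects, a qualifying event in Cycle 1, and attribution as at least possibly related to duvelisib. The documents give no probability for any of these. Section 6.7.1 also lets the investigator and sponsor document why a qualifying event is not counted.
- *That a site running only PCR would miss subjects due for CMV monitoring.* Section 6.5.1 ties monitoring to a history of infection, reactivation or viremia. It does not mention seropositivity, and medical history is collected separately at Screening.

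**Conclusion.** The concern holds as an internal inconsistency. The criterion is defined by viral load, the required screening tests may all be completed without measuring it, and Table 23 differs from Tables 1 and 3 on EBV. Following the plan as written can lead to dosing a subject whom the plan excludes.

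The size cannot be put as a number of subjects. It depends on how often viremia is present and unrecognised in this population and on which test sites choose, and the documents give neither. The conclusion rests on the natural reading of the Table 23 sentence for EBV. Under the wider reading the difference between tables narrows, but the main point is unchanged. The 13 plus 17 subject design, its decision rules and its error rates are not affected. This should be corrected because it bears on subject safety and is inexpensive to repair; it does not call the trial's statistical design into question.

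**What to change.** Reconcile exclusion 12 with the viral-screening entries in Tables 1, 3 and 23, so that the test required at Screening decides the criterion for CMV and for EBV before the first dose, and so that the three tables name the same tests. Table 23 already contains a usable pattern in its hepatitis B entry, where an antibody result leads to a DNA test before dosing. Whether to follow that pattern, require viral load in everyone, or restate the criterion is for the sponsor to decide. The wording of Table 12 should be read alongside whichever choice is made.

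The cost is amended wording in three tables and a blood test that the schedules already list as an option. Some additional screen failures are possible; their number cannot be estimated from the documents. Sample size and analysis need no change.
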